4.2. Participant recruitment

Only hospitalized COVID-19 patients are eligible so recruitment efforts will be focused on identifying consecutive patients admitted to hospital with acute COVID-19 infection. No other external recruitment efforts are planned. At each participating hospital, a process for immediately identifying admitted patients with COVID-19 will be established. The mechanism of alerting the research assistants (RA) will be determined by local site principal investigator.

Patients who are confirmed to have COVID-19 infection and are admitted to hospital will be assessed for eligibility. Consent may be obtained verbally, given the infection control precautions

in place for these participants, as permitted by local research ethics committees. The RA (or a bedside physician if deemed acceptable by local research ethics boards [REB]) will obtain consent from the patient or legally authorized representative (LAR) by phone or videoconference. After consent is obtained, the RA will confirm eligibility remotely through a review of the electronic medical record and discussion with the bedside physician/nurse. Informed consent will be obtained remotely and may use a variety of visual aids (video brochure, a visual decision board). Documented written consent will be obtained from the patient or LAR as soon as possible as required by local REBs. At the time of assessing eligibility the RA will confirm with the site storing CCP that an ABO-compatible CCP plasma unit is available (for certain sites, group A plasma with low-titer anti-B (≤1:50) is allowed to be transfused to group B or AB patients). If 500 mL of CCP is available and eligibility criteria are met, the RA will randomize the patient. The RA will notify the blood bank of the allocation and a marker will be placed in the Laboratory Information System and the patient chart indicating that the patient is enrolled in the CONCOR-1 trial. For patients randomized to CCP, the RA will notify the bedside physician to order the study product. The CCP will be thawed in the blood bank, issued, and infused by the bedside nurse within 24 hours of randomization.

4.3. Randomization Procedures

Patients will be randomized in a 2:1 ratio (CCP to standard of care). Patients will be randomized using a secure, concealed, computer-generated, web-accessed randomization sequence. Randomization will be stratified by centre and age (<60 and ≥ 60 years). Within each stratum, variable permuted block sizes will be used. This approach will ensure that concealment of the treatment sequence is maintained.

4.4. Intervention:

Patients will be assigned to the experimental treatment (CCP) or the control (standard of care).

4.4.1. CCP

Patients will receive approximately 500 mL of CCP (from one single-donor unit of 500 mL or 2 units of 250 mL from one or two donors) collected by apheresis from donors who have recovered from COVID-19 and frozen (1 year expiration date from date of collection). The plasma unit will be thawed as per standard blood bank procedures and infused into the patient slowly over 4 hours or as per local procedures. When administering 2 units of 250 mL, the 2nd unit should be administered immediately after the first unit, and we recommend that it should be given within 12 hours after the first unit. The patient will be monitored for adverse events as per each site's policies. Details regarding the CCP are summarized in Section 5.0.

4.4.2. Standard of Care

Patients receiving standard of care will receive all medical care as per routine practices at each site.

4.5. Participant Withdrawal and Discontinuation of IP

Subjects in this clinical trial may discontinue the investigational product for any of the following reasons:

- Subject requests to discontinue the investigational product during transfusion or to be removed from clinical trial activities for any reason (reason for withdrawal will be requested)
- Occurrence of any medical condition or circumstance that exposes the patient to substantial risk and/or does not allow the patient to adhere to the requirements of the protocol
- Any SAE, clinically significant AE, severe laboratory abnormality, intercurrent illness, or other medical condition deemed related to the investigational product that indicates to the Investigator that continued participation is not in the best interest of the patient (in such case the investigational product must be discontinued).
- Patient fails to comply with protocol requirements or study-related procedures

Unless the patient withdraws consent, those who discontinue the investigational product during the infusion should remain in the study and be included in the intention-to-treat population. The reason for participant discontinuation of investigational product should be documented in the case report form where known.

Should the participant withdraw consent or requests discontinuation for any reason, whenever possible, the patient or LAR will be asked if the patient can be followed for outcome and safety evaluations (where permitted by the local REB).

4.5.1. Data Collection and Follow-up for Withdrawn Participants

Participants who withdraw from this study or who are lost to follow-up after randomization will not be replaced. The reason for patient discontinuation from the study will be recorded on the appropriate case report form. In the case of a participant's lost to follow-up, attempts to contact the patient will be made and documented in the patient's study file.

4.6. Blinding and Unblinding Procedures

This is an open-label trial. The decision to perform the trial unblinded was based on the following reasons: (1) to allow for participation of academic and non-academic hospital sites where masking procedures are not possible given the required short implementation timelines; (2) to avoid exposing patients to the risks of a standard plasma arm as the placebo has no anticipated benefit; (3) to avoid the need to create an inert placebo (e.g. coloured saline) including the need to mask, which would cause significant disruption of workflow and additional use of PPE during the pandemic.

4.7. Number of Study Centers

The number of hospital sites across Canada will be ~40-60 sites, including sites in every Province and potentially every territory in both academic and community-based hospitals. There will be a

gradual onboarding of sites starting with larger centres in Québec and Ontario where the burden of the pandemic is expected to be the largest. We will use Clinical Trials Ontario (CTO), the central REB for Ontario sites and expedite time to first patient treated. The multi-centre ethics evaluation process will be similarly used in Québec. Thereafter sites will be on-boarded based on size and the current distribution of cases of COVID-19 to ensure the greatest access to the trial based on need. In addition, to enhance the rapidity of study enrollment, one New York City Institution in the U.S. will participate, as well as several sites in Brazil and one site in Israel.

4.8. Subject Identification and Randomization

4.8.1. Subject Identification

Subjects in this study will have specific screening number. Subjects failing screening will retain their screening number. The screening number for each subject will be a combination of the site number plus a number assigned to the subject according to her/his chronological order of screening at that site. The screening number will be used as the subject identifier throughout the study.

4.9. Interim Analysis

A single interim analysis is planned when the primary outcome (intubation or mortality at Day 30) is available for 50% of the target sample. An O'Brien- Fleming stopping rule⁴⁴ will be used at that time, but treated as a guideline, so there is minimal impact on the threshold for statistical significance for the final significance test of the primary outcome.

5. INVESTIGATIONAL TREATMENT

5.1. Identity

The investigational product consists of approximately 500 mL Apheresis Frozen Plasma (AFP) collected from patients who have recovered from COVID-19.

5.2. Mechanism of action

Transfusion of AFP from COVID-19 convalescent patients allows the transfer of donor neutralizing antibodies directed against SARS-CoV-2 antigens in the recipient, thus allowing the generation of passive immunization. Naturally produced human antibody are polyclonal, meaning they are directed against a variety of different viral antigens and epitopes allowing for a general neutralizing effect against the virus rather than focussing on a specific target. Administration of CCP has been associated with rapid decrease in viral load. It is also possible that passive immunization contributes to improved cell-mediated immunity by favoring the phagocytosis and presentation of viral antigens to host T cells.

5.3. Approved indication

5.3.1. Approved Indications for Canada and Israel

AFP transfusions are currently indicated in Canada for the management of:

- 1. Bleeding patients or patients undergoing invasive procedures who require replacement of multiple plasma coagulation factors
- 2. Patients with massive transfusion with clinically significant coagulation abnormalities
- 3. Patients on warfarin who are bleeding of need to undergo an invasive procedure before vitamin K could reverse the warfarin effect, and where prothrombin complex concentrate is not available or is contraindicated
- 4. Patients with selected coagulation factor or with rare specific plasma protein deficiencies for which a more appropriate alternative therapy is not available
- 5. Preparation of reconstituted whole blood for exchange transfusion in neonate
- 6. Patients with thrombotic thrombocytopenic purpura (TTP) or hemolytic uremic syndrome (HUS) undergoing plasma exchange

5.3.2. Approved Indications for the United States and Brazil

AFP transfusions are currently indicated in the United States for the management of:

- 1. Preoperative or bleeding patients who require replacement of multiple plasma coagulation factors (eg. Liver disease, DIC).
- 2. Patients undergoing massive transfusion who have clinically significant coagulation deficiencies.
- 3. Patients taking warfarin who are bleeding or need to undergo an invasive procedure before vitamin K could reverse the warfarin effect or who need only transient reversal of warfarin effect.

- 4. Transfusion or plasma exchange in patients with thrombotic thrombocytopenic purpura
- 5. Management of patients with selected coagulation factor deficiencies, congenital or acquired, for which no specific coagulation concentrates are available.
- 6. Management of patients with rare specific plasma protein deficiencies, such as C1 inhibitor, when recombinant products are unavailable.

5.4. Acquisition, Formulation and Packaging

For Canadian sites, the investigational product will be provided by Héma-Québec and Canadian Blood Services. For United States sites, the investigational product will be provided by the New York Blood Center (NYBC). For Brazilian sites, the investigational product will be provided by Hemorio. For the Israeli site the product will be provided by the Magen David Adom National Blood Services.

5.4.1. **Donor recruitment**

5.4.1.1. Donor recruitment for Canadian Sites

Recovered COVID-19 patients will be identified as potential donors in collaboration with provincial public health services, local health authorities and individual co-investigators involved in the study. Potential donors may also be recruited following self-identification on the routine donor questionnaire or through social media. They will be contacted by phone and invited to participate in the program as potential donors. After obtaining consent and reviewing donor selection criteria, eligible participants will be directed to a Héma-Québec collection or Canadian Blood Services apheresis collection site in their area to donate.

Criteria for donors: All donors will need to meet the criteria set forth in the Manuals of donor selection criteria in use at Héma-Québec or Canadian Blood Services.

In addition, donors will require:

- Prior diagnosis of COVID-19 documented by a PCR test at time of infection or by positive anti-SARS-CoV-2 serology following infection
- Male donors, or females with no pregnancy history or with negative anti-HLA antibodies
- At least 6 days since last plasma donation
- Provided informed consent
- A complete resolution of symptoms at least 14 days prior to first donation.

Criteria for donation are subject to change based on future revision of Health Canada guidance.

5.4.1.2. Donor recruitment for United States Sites

Recovered COVID-19 patients are being recruited through the New York Blood Center and Weill Cornell Medicine in separate protocols. Potential donors can self-refer via websites but also be referred by physicians or identified via the medical record system. Only donors with laboratory-confirmed history of COVID-19 will be screened. After providing consent and reviewing FDA and

NYBC donor eligibility criteria, donors are screened for the presences of SARS-CoV-2 virus in the nasopharynx if screening within 14 days of complete resolution in accordance with current FDA guidance. Criteria for donation are subject to change based on future revision of FDA guidance. Those found to be eligible will be referred to NYBC for donation.

Criteria for donors:

- Provision of informed consent
- Aged 18 to 70 years. Donors are not longer eligible after their 71st birthday.
- Documented molecular diagnosis of SARS-CoV-2 by RT-PCR by nasopharyngeal swab, oropharyngeal swab, or sputum or detection of anti-SARS-CoV-2 IgG in serum.
- Complete resolution of COVID-19 symptoms at least 14 days prior to donation
- Not currently pregnant or pregnant within 6 weeks by self-report
- Male donors, or females with no pregnancy history or with negative anti-HLA antibodies
- Meets blood donor criteria specified by NYBC, which is consistent with FDA regulations.

Donors will be allowed to donate every 7 days. The following information will be collection from donors: ABO group, sex, age, date of onset of symptoms (when available), date of resolution of symptoms (when available) and CCP collection date(s).

Sterile segments of frozen plasma will be attached to all units consisting of at least 2 mL of plasma volume. These segments will be submitted to the Centre Hospitalier de l'Université de Montréal Research Center for testing of SARS-COV-2 antibody titer and neutralizing antibody titer.

5.4.1.3. **Donor recruitment for Brazil**

Recovered COVID-19 patients will be identified as potential donors in collaboration with provincial public health services, local health authorities, individual co-investigators involved in the study. Potential donors may also be recruited following self-identification on the routine donor questionnaire or through social media. They will be contacted by phone and invited to come to Hemorio in order to undergo a medical examination that will include the collection of blood samples. If they are approved as plasma donors, after obtaining consent, they are invited to make an appointment to come back and donate plasma, as soon as possible.

Criteria for donors: All donors will need to meet the criteria set forth in the Manuals of donor selection criteria in use at Hemorio and in Brazilian specific regulations.

In addition, donors will require:

- Aged 18 to 60 years. Donors are no longer eligible after their 61st birthday
- Prior diagnosis of COVID-19 documented by a PCR test at time of infection or by positive anti-SARS-CoV-2 serology following infection
- Male donors, or females with no pregnancy history or with negative anti-HLA antibodies
- At least 7 days since last plasma donation
- Provided informed consent

- 7-day interval between each donation, limited to 4 donations over a 2 month period
- A complete resolution of COVID-19 symptoms at least 14 days prior to first donation.

Criteria for donation are subject to change based on future revision of Brazilian federal regulation.

5.4.1.4. **Donor recruitment for Israel**

Recovered COVID-19 patients will be identified as potential donors in collaboration with national health services, local health authorities and individual co-investigators involved in the study. Potential donors may also be recruited following self-identification on the routine donor questionnaire or through social media. They will be contacted by phone and invited to participate in the program as potential donors. After obtaining consent and reviewing donor selection criteria, eligible participants will be directed to the Magen David Adom National Blood Services apheresis collection site in their area to donate.

Criteria for donors: All donors will need to meet the criteria set forth in the Manuals of donor selection criteria in use at Magen David Adom National Blood Services

In addition, donors will require:

- Prior diagnosis of COVID-19 documented by a PCR test at time of infection or by positive anti-SARS-CoV-2 serology following infection
- Male donors, or females with no pregnancy history or with negative anti-HLA antibodies
- At least 14 days since last plasma donation
- Provided informed consent
- A complete resolution of symptoms at least 14 days prior to first donation.

Criteria for donation are subject to change based on future revision of Israel Ministry of Health guidance.

5.4.2. Acquisition and Formulation

5.4.2.1. For Canadian Sites

Plasma will be collected by apheresis from qualified donors who have consented to donate, using the equipment and technologies already in operation at Héma-Québec and Canadian Blood Services following standard operating procedures.

Because apheresis collection allows for plasma only collection while blood cells are returned to the donor, donor are eligible to donate every 6 days (at minimum). This will permit the collection of CCP from the same donor at weekly intervals. SARS-CoV-2 antibody titers will be monitored at each donation to ensure the presence of sufficient amounts of antibody for the treatment of patients suffering from COVID-19.

Plasma collection using the TRIMA® Accel™ technology (Terumo BCT)

The TRIMA® Accel™ technology allows the automated collection of different blood components and contains programs for plasma collection only. Disposable sterile kits for plasma collection are available (kits with 3 or 4 plasma bags). Depending on the donor characteristics (calculated blood volume), plasma volumes up to 750 mL can be collected. The procedure starts with the collection of a small volume of blood in a sampling bag; this blood will be used for regulatory analyses at Héma-Québec and Canadian Blood Services (transfusion transmissible diseases) and to establish the anti-SARS-CoV-2 seropositivity. During collection, blood is mixed with ACD-A (anticoagulant citrate dextrose, solution A), plasma is separated from blood cells by centrifugation and collected in 2 or 3 bags (depending on the target volume that has been predefined) based on the estimated total blood volume of the donor whereas blood cells are returned to the donor.

Plasma collection using the PCS®2 technology (Haemonetics)

This automated system is used to collect plasma only. Samples required for regulatory analyses and antibody seropositivity determination are taken directly from the collected unit after plasma collection is completed. During collection, blood is mixed with anticoagulant (sodium citrate 4%) to avoid clotting and centrifuged in a single use, sterile centrifugation bowl to separate plasma from blood cells. When separation is completed, plasma is automatically transferred to the collection bag and thereafter, blood cells are returned to the donor.

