12. STATISTICAL CONSIDERATIONS

12.1. Sample Size Considerations

Assuming a baseline risk of intubation or death by Day 30 of 30% in hospitalized patients with standard of care, a sample size of 1200 (800 in the CCP arm, and 400 in the standard of care arm) would provide 80% power to detect a relative risk reduction of 25% with CCP therapy using a 2-tailed test at level α = 0.05. This assumes no patient is lost to follow-up. Lost follow-up is expected to be minimal.

There is uncertainty about the intubation and mortality rate that will be observed in this study due to possibly evolving profile of COVID-19 patients admitted hospital over the course of the pandemic. To address this, a blinded sample-size re-estimation will take place when the primary outcome is available for 50% of the target sample. Sample size will only be adjusted if the estimated event rate is different than the originally specified event rate to a sufficient extent that the study is not expected to achieve the desired nominal power for the test of the primary outcome.

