12.4.5. Exploratory Analysis

Association between anti-SARS-CoV2 antibody in CCP and the primary outcome of intubation or death will be assessed using logistic regression. Anti-SARS-CoV-2 antibodies will be characterized according to the amount of antibodies against the native spike protein and the RBD, as well as to their neutralizing and Fc functions. Exploratory analyses will also examine possible associations between donor characteristics and treatment efficacy. Change in viral load and in anti-SARS-CoV2 serology in the recipient following transfusion will also be assessed and correlated with treatment outcome.

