2 STATISTICAL ANALYSES INVOLVING LABORATORY DATA

As a preliminary analysis we will tabulate the availability of marker data by site, blood provider, and according to the type of the marker. A careful description of the units used to measure the markers will be carried out with any change of units carried out as required. Upon standardization of the scales the summary statistics will be computed for each marker by site, by provider, and overall. All of the analyses that follow will control for the provider as a factor variable to ensure that comparisons are made within providers. This variable is suppressed in the model statements that follow for convenience.

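### Several CCP recipients can share one donor, but the marker models have no donor term, so their confidence intervals may be too narrow

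*Protocol*

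**What the plan says.** **Supply.** Protocol 5.4.2.1 sets a minimum of six days between Canadian donations and adds: "This will permit the collection of CCP from the same donor at weekly intervals". Section 5.4.2.2 allows US donation every 7 days. For Brazil, section 5.4.1.3 sets a "7-day interval between each donation, limited to 4 donations over a 2 month period". Israel has a 14-day minimum (5.4.1.4 and 5.4.2.4); section 5.4.2.4 also speaks of weekly collection, which must be reconciled, but nothing below depends on it. With one of the Canadian collection systems, "plasma volumes up to 750 mL can be collected" in a session; the Brazilian figure is 600 mL (5.4.2.3). A dose is about 500 mL, taken "from one single-donor unit of 500 mL or 2 units of 250 mL from one or two donors" (4.4.1). No section caps the number of recipients per donor.

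**Analysis.** SAP 4.6.1 and Supplement 2.1 to 2.4 fit logistic regressions, and in the Supplement also generalized additive models, with one record per recipient. Supplement section 2 names one grouping variable: "All of the analyses that follow will control for the provider as a factor variable to ensure that comparisons are made within providers". Supplement 1.5.1 averages repeat assays of a donor's plasma but says nothing about recipients who share a donor. SAP 4.4 plans within-subgroup intervals and p-values by donor illness severity, without a donor term. Protocol 12.4.5 adds: "Exploratory analyses will also examine possible associations between donor characteristics and treatment efficacy". It names no model for that part.

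**The concern.** A marker or donor trait belongs wholly or partly to the donor, so recipients of one donor's plasma have similar values. If anything else about that plasma affects outcome, it sits in the error term and is also shared. Model-based standard errors then overstate the information available. A provider factor does not help, because donors are nested within providers.

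The trial's own rationale makes residual correlation plausible. Protocol 1.2 notes that assays of different antibody functions may disagree and complement one another. Protocol 5.6 says that no clinically validated measure of plasma potency exists. Yet Supplement 2.1 and 2.2 begin with one marker at a time, which leaves the other three in the error term.

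What is at stake is the answer to which plasma works. SAP 4.8 counts the effect of neutralizing antibodies among the important secondary questions that the trial should be large enough to address. SAP 4.6.1 sends these analyses to the IDSMC at the interim. Supplement 2.2 uses the additive models to look for marker cut-offs. Bands that are too tight could suggest a cut-off that the data do not support.

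**Working it through.** **1. The plan's own figure.** Protocol 12.1 gives 800 against 400 patients, 30% control risk, a 25% relative reduction (so 22.5% on CCP), two-sided 0.05 and 80% power.
- Pooled risk: (0.30×400 + 0.225×800)/1200 = 0.25.
- Null SE: √(0.25×0.75×(1/400+1/800)) = 0.0265.
- Alternative SE: √(0.30×0.70/400 + 0.225×0.775/800) = 0.0273.
- Power: Φ((0.075 − 1.96×0.0265)/0.0273) = 80.1%.

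The figure reproduces (78.6% with the unpooled Wald form). It concerns the primary comparison. The documents give no figure for the marker models.

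**2. Can donors be shared?** A 750 mL session is 750/500 = 1.5 doses. Four 600 mL sessions, the two-month Brazilian cap, are 2400/500 = 4.8 doses. Eight doses (4000 mL) need six 750 mL sessions, which fit in 5×6 = 30 days at the Canadian minimum interval. These are ceilings on capacity, not expected use.

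**3. Inflation formula.** Let m be recipients per donor, ICC the residual within-donor correlation of outcome, and r the within-donor correlation of the marker.
- Design effect: DE = 1 + (m−1)×ICC×r.
- Understatement of the SE: factor √DE.
- True two-sided error of the unadjusted test: 2×(1 − Φ(1.96/√DE)).

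m, ICC and r are assumptions. r = 1 (exposure fully donor-determined) gives an upper bound.

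Example with m=8, ICC 0.10, r=1: DE = 1 + 7×0.10 = 1.70; √DE = 1.304; error = 2×(1 − Φ(1.503)) = 13.3%; effective sample 800/1.70 = 471.

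| m | ICC | Error, r=1 | Error, r=0.6 |
|---|---|---|---|
| 2 | 0.01 to 0.10 | 5.1% to 6.2% | 5.1% to 5.7% |
| 4 | 0.01 to 0.10 | 5.3% to 8.6% | 5.2% to 7.1% |
| 8 | 0.01 to 0.10 | 5.8% to 13.3% | 5.5% to 10.0% |

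**4. Simulation check.** Logistic regression on 800 CCP recipients with 22.5% events, one donor each, r=1, 3000 runs:

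| m | ICC | Unadjusted test | Donor-cluster-robust |
|---|---|---|---|
| 4 | 0.05 | 6.2% | 5.1% |
| 4 | 0.10 | 8.3% | 5.2% |
| 8 | 0.05 | 8.9% | 6.2% |
| 8 | 0.10 | 12.0% | 5.2% |

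With two donors per recipient (1500 runs, same ratio of recipients to donors, r=1), the unadjusted error at ICC 0.10 was 7.4% for m=4 and 9.3% for m=8. With one donor per recipient and ICC=0, the unadjusted test ran between 4.8% and 6.3%, so differences of about a point should not be read closely.

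**The case against.** The strongest reply is that sharing is permitted, not shown, and that the larger figures need strong assumptions.

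- **m is unknown.** The documents say what donors may do, not how many recipients each supplied. This stands.
- **The ICC range reaches high.** At 22.5% risk, the between-donor SD in risk is √(ICC×0.225×0.775): 4.2 points at ICC 0.01 and 13.2 at ICC 0.10. The trial is powered for 7.5 points in all. A reader who assumes uneven donor use (mean 8) and an omitted donor factor of odds ratio 1.5 to 2.0 per SD reaches 10-19% error. That needs one SD of an unmeasured trait to match or exceed the whole design effect, which is an odds ratio of (0.30/0.70)/(0.225/0.775) = 1.48. The documents give no ground for it.
- **Markers are not purely donor-level.** SAP 4.6.1 tests every transfused unit, and Supplement 1.5.2 forms a volume-weighted dose per recipient. This stands, so the r=1 column is an upper bound for the markers.
- **Two-donor dosing dilutes the effect.** It generally does, without removing it.
- **Joint models leave less in the error term.** SAP 4.6.1 and Supplement 2.1 and 2.3 also fit markers together. The concern is weaker there, and it was not quantified.
- **Clustered errors are imperfect.** With 100 donors and no correlation, the robust test reached 6.9% in simulation. Hence the small-sample correction below.

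None of this supplies the missing donor term. The provider factor cannot, and the independence assumption is neither stated nor checked.

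**Conclusion.** The omission is real and its effect is conditional. In SAP 4.6.1, Supplement 2.1 to 2.4 and the donor-severity subgroup of SAP 4.4, intervals may be too narrow if recipients sharing a donor keep correlated outcomes after the modelled marker and provider. Over the assumed ranges the effect runs from negligible to rather more than a doubling of the 5% error (13.3%, at m=8, ICC 0.10 and r=1). With m=1 or ICC=0 there is no inflation.

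The documents do not support three stronger readings that a reader might infer:
- That the intervals are known to be too narrow. Neither m nor the ICC is given.
- That every donor-characteristic model assumes independence. Protocol 12.4.5 names no model for those analyses, so their handling is unspecified rather than wrong.
- That the primary result is compromised. It compares the randomized arms, not donor-level exposures. If plasma makes no difference to any recipient, sharing a donor through it cannot correlate their outcomes. The stated sample size is not in dispute.

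For exploratory analyses this is a modest but worthwhile improvement.

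**What to change.** 1. Ask each supplier for a de-identified donor code with the unit data of Protocol 8.1. That section does not name one, though its list of donor items is only illustrative. Labels in the US, Brazil and Israel already carry a donor identification number (5.5.2 to 5.5.4).
2. Report the number of donors and the distribution of recipients per donor. This alone may show that the issue is negligible.
3. In SAP 4.6.1, Supplement 2.1 to 2.4 and the donor-characteristic analyses, including the donor-severity subgroup, base inference on the donor. Use either cluster-robust standard errors with a small-sample correction, or a donor random effect with volume-weighted multiple membership for two-donor recipients. In models that include the control arm, treat each control patient as a separate cluster.
4. Use a donor-level bootstrap for the additive-model bands.
5. Keep provider as a fixed factor.

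The cost is one coded field, a short addition to the SAP and Supplement, and somewhat wider intervals in exploratory analyses. If sharing proves rare, the results should change little.
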